4.3. Analysis Sets

4.3.1. Patient Sets

- Non-included patients: all patients who are not included in the study (as recorded in the non-inclusion register).
- Included patients: all patients included in the study.
- Safety analysis set: all patients included in the study who received at least one dose of the documented treatment (the treatment start date must be entered) in the study (targeted therapy or other treatment). If the patient is prevalent, the treatment must

still be ongoing at the time of inclusion in the study and if the patient is incident, the treatment must be started at or after inclusion in the study.

• Reference set (Full Analysis Set): patients included who meet the eligibility criteria and have received at least one dose of the treatment documented during the prospective follow-up period (the treatment start date must be completed and the treatment stop date must be after the date of inclusion if the start date is prior to the date of inclusion) in the study (targeted therapy or other treatment). Patients with no follow-up data will be excluded from this population.

Two treatment groups will be analysed: the "targeted therapy" with two subgroups, everolimus (AFINITOR®) and sunitinib (SUTENT®); and an "other treatments" group with four subgroups: chemotherapy, somatostatin analogs, interferon-alpha and metabolic radiotherapy.

4.3.2. Doctor Sets

- Active doctors: who have included at least one patient.
- Inactive doctors: doctors who have not included any patients.

4.4. Protocol Deviation

Deviations from the protocol will be defined from the CRF database. They will be defined and identified prior to the data review meeting and will be reviewed during this meeting.

In particular, deviations from the following inclusion and non-inclusion criteria will be identified for the data review:

- Breach of inclusion criteria defined below:
 - Patients over 18 years old,
 - Patients treated with a targeted therapy (Sunitinib, Everolimus) or with other treatments (interferon or metabolic radiotherapy or chemotherapy or somatostatin analog)* for:
 - an unresectable or metastatic histologically confirmed pancreatic neuroendocrine tumour,
 - well differentiated,
 - in progression before treatment is started in the opinion of the investigator (clinical or radiological progression),

*patients whose treatment line (targeted therapy or other treatment) is started 1st, 2nd, 3rd or 4th line at the time of inclusion (patient 'incidents') or patients during their 1st, 2nd, 3rd or 4th line of treatment, provided that treatment was started in the centre in which the patient was included in the study ('prevalent' patients): a change in treatment line is defined as a change in molecule or combination.

- Patients who have been informed of the details of the study and have given their signed consent.
- Breach of non-inclusion criteria defined below:
 - Patients with a diagnosis of poorly differentiated neuroendocrine carcinoma or -neuroendocrine adenocarcinoma.
 - Patients receiving a targeted therapy (Everolimus or Sunitinib) already received during a previous treatment line (re-challenge patient).
 - Patients who refuse to give their consent.
 - Patients treatment fifth line of systemic treatment or above.
 - Patients participating in a clinical study in a treatment arm not approved by the MA and TNCD, versions dated December 2013.
 - Patients randomised into the placebo arm of a placebo-controlled study or into a double-blind study.
- No follow-up data available.

4.5. Handling of Missing Values

In general, missing values will not be used either in calculating the percentages or in computing statistical tests.

The number of missing values for each analysed variable will be shown in the summary tables. Key data will be mandatory in the electronic CRF in order to control the proportion of missing data.

Dates, only used to calculate time periods:

- For the data of birth, the day is not requested in the CRF and will be replaced by 15.
- For calculations involving dates:
 - If the day is missing, it will be replaced by day 15 of the month;
 - If the month and day are missing, they will be replaced by 30 June of the year;
 - If the date is completely missing, it will not be replaced.

These rules will be used if they do not create inconsistencies (negative time intervals). Otherwise the time interval will be deemed to be missing.

The other specific management requirements for missing data are described in the relevant sections of this document.

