3.4 Safety – onset of adverse events
Has the patient experienced adverse events since the last documented visit on [date of last tumour assessment]
visit entered]? ☐ Yes ☐ No
If yes, please describe all adverse events experienced in the Safety section of the eCRF (see 5. Adverse events recording module)
4. Anticipated end of study form
STATUS OF PATIENT
☐ Alive date of last contact: ☐ / ☐ / ☐ (DD/MM/YYYY) Main reason for stopping the study
Does not meet the inclusion criteria at enrolment - exclusion
□ Patient's decision
☐ Transferred to another treatment centre not participating in the study
Other reason, please state:
□ Lost to follow-up date of last contact: □□/□□/(DD/MM/YYYY)
□ Deceased*
◆ If deceased, please state Date of death
Study medication(s) at the time of death
□ Sunitinib
□ Everolimus
☐ Octreotide ☐ Other treatment, please state:
☐ Chemotherapy
☐ Interferon alpha
☐ Somatostatin analogue other than Octreotide
☐ Radionuclide therapy
Cause of death
☐ Disease progression ☐ Adverse event* not related to a study medication
☐ Adverse event* related to a study medication
,
*Places complete the reference tion of the CDF
*Please complete the safety section of the CRF TREATMENT ONGOING WHEN PATIENT LAST SEEN
THEATMENT ONGOING WHEN FAMILY EAST SEEN
If the anticipated end of study form is completed at a time other than a follow-up visit:
Therapeutic management between the last documented tumour assessment visit on [date of the last documented
visit] and up to the anticipated end of study date:
→ Display section 3.3 Therapeutic management since last tumour assessment
→ Display Table 5 and the screens corresponding to each recorded treatment line
DISEASE OUTCOME

Novartis Pharma S.A.S. - Pfizer S.A.S

Page 85 of 90

Observational study protocol $final\ version\ of\ 17/07/2018$

Best response to treatment when patient	last seen	
☐ Complete response	☐ Stable disease	
☐ Partial response	☐ Disease progression	
Date of the last disease assessment: \\ \\ \ \ \ \ \ \ \ \ \ \ \ \ \ \ \ \		

Please complete the adverse events table for all events reported since inclusion in the study: Description of the adverse event: Table 4 - Safety											
Description the event		Date onset	of	Outcome	Severity	CTCAE grade	Seriousn ess	Causality of the study treatment	Action concerning the study treatment		
History of	pre	viously	des	cribed adverse events	s						

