5.5.2. Best Response to the Treatment at Inclusion and During Follow-up

The best response to the main treatment at inclusion with targeted therapy or other treatment (ongoing at the time of patient inclusion into the study) will be described by analysis group (targeted therapy or other treatment) then according to targeted therapy, chemotherapy and somatostatin-analogs groups.

In addition, the best response during follow-up will also be described overall.

The following ranking will be used in order to define this variable:

complete response>partial response>clinical response>stable disease>disease progression

Data will be deemed to be missing if they have not been completed, or if the "un-assessable" box is checked.

The criterion used in this analysis will be the RECIST criterion if available or the clinician's assessment if it is not.

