Using a similar template:

Table 14.2.1.3: Analysis of Progression-Free Survival – Reference Set – Targeted Therapy Groups

Table 14.2.1.4: Analysis of Progression-Free Survival – Reference Set – Other Treatments Groups

Table 14.2.1.5: Analysis of Overall Survival – Reference Set – Overall

Table 14.2.1.6: Analysis of Overall Survival – Reference Set – Targeted Therapies Group Vs Other Treatments

Table 14.2.1.7: Analysis of Overall Survival – Reference Set – Targeted Therapies Groups

Table 14.2.1.8: Analysis of Overall Survival – Reference Set – Other Treatments Groups

^{*} Event related to main treatment at inclusion.

Programmer note:

- The Kaplan-Meier curves associated with the analyses.
- Show the 95% confidence interval (log-log transformation) of the survival function for the total population analyses.

Table 14.2.1.9: Best Overall Response to the Main Treatment At Inclusion – Reference Set – Analysis Based on Targeted Therapies and Other Treatments

		Targeted therapies (N=XX)	Other treatments (N=XX)	Total (N=XX)
Best overall response	N	XX	XX	XX
•	Missing data	XX	XX	XX
	CR	XX (XX.X%)	XX (XX.X%)	XX (XX.X%)
	PR	XX (XX.X%)	XX (XX.X%)	XX (XX.X%)
	Clinical response	XX (XX.X%)	XX (XX.X%)	XX (XX.X%)
	SD	XX (XX.X%)	XX (XX.X%)	XX (XX.X%)
	PD	XX (XX.X%)	XX (XX.X%)	XX (XX.X%)

Using the same template:

Table 14.2.1.10: Best Overall Response with Main Treatment at Inclusion – Reference Set – Analysis by Treatment Subgroup

Table 14.2.1.11: Best Overall Response During Follow-Up – Reference Set

		Total (N=XX)
Best overall response	N	XX
•	Missing data	XX
	CR	XX (XX.X%)
	PR	XX (XX.X%)
	Clinical response	XX (XX.X%)
	SD	XX (XX.X%)
	PD	XX (XX.X%)

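### Best-response percentages run over assessed patients only, and the tables have no row for patients never assessed

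*SAP*

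**What the plan says.** SAP 4.5 states that, as a general matter, "missing values will not be used either in calculating the percentages or in computing statistical tests". It leaves other specific rules to the relevant sections, and it promises disclosure: "The number of missing values for each analysed variable will be shown in the summary tables".

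The relevant section here is SAP 5.5.2. It ranks the outcomes as "complete response>partial response>clinical response>stable disease>disease progression" and has no category for a patient who could not be evaluated. On gaps it says "Data will be deemed to be missing if they have not been completed", and it treats a ticked un-assessable box the same way. It also names a second source: "The criterion used in this analysis will be the RECIST criterion if available", and otherwise the clinician's assessment.

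The shell in SAP 9.2 for Table 14.2.1.9, titled "Best Overall Response to the Main Treatment At Inclusion", has rows for N, missing data (count only) and the five outcomes (count and percentage). Table 14.2.1.10 uses the same template, and Table 14.2.1.11 has the same rows in a single total column. All three use the reference set, for which SAP 4.3.1 adds: "Patients with no follow-up data will be excluded from this population".

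In the protocol's case report form, the anticipated end of study form has a field beginning "Best response to treatment when patient". It offers complete response, partial response, stable disease or progression.

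**The concern.** Tumour assessments follow usual practice, about every two to three months (Protocol 5.2.1). A patient who dies, or stops the inclusion treatment, before the first assessment may have no response recorded on that treatment. Such a patient is more likely to be a treatment failure than a responder. Leaving these patients out of the denominator then makes the response percentages look better than they would in the whole group.

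Tables 14.2.1.9 and 14.2.1.10 show best response by treatment group and subgroup. The Protocol's justification section records that the health authority wanted data on the targeted therapies set against other treatments, so readers will look across the columns.

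The SAP is more cautious elsewhere. When seriousness or causality of an adverse event is missing, SAP 5.7.2 assumes the reading least favourable to the treatment. For best response no conservative rule is given. SAP 6.3 says only that missing-data handling will be discussed and approved before the analyses.

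**Working it through.** **Which denominator applies.** SAP 4.5 removes missing values from percentages unless a specific section says otherwise. SAP 5.5.2 defines what is missing and says nothing about the denominator. The shells attach no percentage to the missing row and carry no footnote setting another base. The general rule therefore governs, and percentages are taken over assessed patients.

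**The plan's own figure.** The documents state no expected response rate and no expected number unassessed. The only figures for a percentage are the precisions in SAP 4.2, which are 95% half-widths, 1.96 × √(p(1−p)/n). For p = 50% this gives 11.3, 8.0 and 6.9 points at n = 75, 150 and 200, as the SAP prints. For p = 25% at n = 75 it gives 1.96 × √(0.25 × 0.75/75) = 9.8 points.

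**Effect of the denominator.** Let N be the patients in the group, m those with no response on any source, r those in a given category, and f = m/N.

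- Printed percentage: r/(N − m)
- Full-set percentage: r/N
- Ratio: N/(N − m) = 1/(1 − f), which is 1.05, 1.11, 1.18 and 1.25 at f = 5%, 10%, 15% and 20%

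The ratio is the same for every row, so progressive disease is scaled up by the same factor as complete response.

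**Size under assumed inputs.** The missing fractions and response rates here are assumptions.

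- Worst case, no unassessed patient responded, true complete-plus-partial response 25%: 0.25/0.90 = 27.8% with 10% missing, and 0.25/0.80 = 31.3% with 20% missing. The shift is 3 to 6 points, inside the 9.8-point half-width at n = 75.
- In whole patients, N = 75 (the SAP's illustrative group size) with 15 responders, 20.0% of the full set: 15/71 = 21.1% with 4 missing, 15/67 = 22.4% with 8, 15/60 = 25.0% with 15.
- Unequal missingness: 15 responders of 75 in both groups, with 4 missing in one and 15 in the other, print as 21.1% against 25.0%.

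**If the worst case does not hold.** Suppose unassessed patients would have responded at the same 25% rate. With 10% missing the assessed-only figure is (0.25 − 0.10 × 0.25)/0.90 = 25%, which is correct, and the full-set figure is 0.225. With 20% missing they are (0.25 − 0.20 × 0.25)/0.80 = 25% and 0.20. The full-set percentage is then the one that errs, downwards.

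**The case against.** The strongest reply is that few patients will be missing.

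- The clinician's assessment stands in when RECIST is absent.
- Protocol 5.2.2 requires an end-of-study questionnaire for every patient who leaves before 24 months. That form covers deaths and includes the best-response field. SAP 8 lists this field and both visit response fields among the key data, and SAP 4.5 makes key data compulsory in the eCRF.
- Stopping treatment does not stop assessment. Visits continue regardless of discontinuation (SAP 3.3), and the case report form keeps untreated patients in follow-up for two years.

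This stands in large part. A reader might infer that early deaths and early stoppers as a class disappear from the tables. The documents do not support that: a patient with progression recorded on any of these sources stays in, as progressive disease. Some gap remains, because a compulsory field cannot supply an assessment that never took place, and SAP 5.5.2 does not say that the end-of-study field feeds the variable.

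A reader might also infer an inflated disease-control rate, for example a true 65% printing as 72–81% (0.65/0.90 and 0.65/0.80). The SAP defines neither an objective-response nor a disease-control rate; both are sums that a reader would form from the rows. Those figures also require every unassessed patient to be a failure. If 30% of them had disease control (also assumed), the print would be (0.65 − 0.03)/0.90 = 69% to (0.65 − 0.06)/0.80 = 74%, and the full-set figures would be 62% and 59%.

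Nor do the documents show that the unassessed fraction differs between targeted therapies and other treatments, so a bias towards either group cannot be asserted. Strict comparison is disclaimed in Protocol 8.3.2.1 and SAP 6.4. Best response is not among the three parameters listed in SAP 5.5, and progression-free and overall survival do not use this rule.

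Finally, the missing count is printed, so a reader can rebuild the full-set percentage by hand. That is true, but it does not change the percentage on the page.

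**Conclusion.** The point holds as one of presentation and denominator. Best-response percentages will be computed over assessed patients, and each will exceed its full-set counterpart by the factor 1/(1 − missing fraction), progressive disease included. That factor is exact arithmetic. Reading it as bias in the response rate rests on the expectation, which the documents do not establish, that patients with no response on any source are mostly non-responders.

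The size cannot be fixed from the documents. With 10–20% unassessed and no responders among them, 25% prints as 28–31%; with fewer missing, or some responders among them, the shift is smaller or nil. Unequal missing fractions would distort the side-by-side columns, in a direction that cannot be predicted. The effect should be smaller in Table 14.2.1.11, which covers the whole follow-up and so picks up assessments made after treatment stops. This is a minor point: the analysis is descriptive and the survival results are untouched.

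**What to change.** In SAP 5.5.2, state that best response is exempt from the general rule in 4.5 and that percentages use all reference-set patients in the group. In Tables 14.2.1.9 to 14.2.1.11, replace the missing-data row with a row for not assessed or un-assessable, giving count and percentage, split by reason where known (for example death before assessment, or stopped before assessment). Keep the assessed-only percentages as supportive.

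The new denominator does not restore patients whom SAP 4.3.1 removes for lack of follow-up data. Report their number by group beside the best-response table; Table 14.1.3.2 already plans that count.

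The cost is a sentence or two in 5.5.2 and a shell edit, with no new data collection. The displayed response percentages become slightly lower, and they are conservative if some unassessed patients had in fact responded.

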4.6. Listings

All listings will include at least the following items:

- Centre number
- Subject number
- Age/Sex
- Documented treatment in the study
- Inclusion data
- Date of first receipt of the documented treatment in the study
- Visit date (if applicable)
- Visit (if applicable)
- Safety analysis set (yes/no)
- Reference set (yes/no)

The functions will be sorted by group (targeted therapy/other treatment), centre number, subject number and visit date (if applicable). Missing data will not be replaced in the listings.

4.7. Derived Variables

• Total duration of exposure to the documented treatment in the study (months)

(Date of last receipt of treatment – Date of first receipt of treatment + 1)/30.4375

For patients who drop out of the study early, the date of last receipt of the treatment considered will be the date of the last visit.

To analyse exposure times by treatment received at least once during the study, if the start date is after the date of the last visit, the treatment will not be considered.

In terms of exposure time for treatments used in combination, the start date and end date of the combination were not recorded in the CRF. The visit prior to the report describing addition of the combination will be deemed to be the start date and the visit in which the combination is reported as being discontinued will be deemed to be the end date for the combination, unless the combination began or finished during a line of treatment (or includes the start and end date).

• In general, the time between two dates expressed in days will be obtained as follows:

Most recent date – Least recent date

The following conversion factors will be used to convert the times into months or years:

- 1 month = 30.4375 days
- 1 year = 365.25 days
- Age (in years) will be calculated as follows:

(Inclusion date – Date of birth)/365.25

• The disease duration (in years) will be calculated as follows:

(Inclusion date – Disease start date)/365.25

• The disease duration (in years) at start of the current treatment at inclusion will be calculated as follows:

(Treatment start date - Diagnosis date) / 365.25

• Time until first temporary discontinuation since inclusion into the study:

(Date of first temporary discontinuation – Date of inclusion + 1)/30.4375

• Time until permanent treatment discontinuation since inclusion into the study:

(Date of final discontinuation – Date of inclusion + 1)/30.4375

• Lines of cancer treatment:

Treatment lines will be defined in two ways:

- Main treatment line: All new treatments will be considered as a new main treatment line.
- Main concomitant treatment line: All new treatments or new combinations will be deemed to be a new concomitant treatment line.

The reason for discontinuing treatment will not be considered in the definition of a treatment line.

The same treatment stopped for over 3 months will be deemed to be two different lines of treatment and to be one line if the discontinuation lasts for less than 3 months.

The treatment lines will be counted differently depending on whether they are a previous treatment or a treatment administered during the study and whether the date of collection is retrospective or prospective.

Prior treatment lines only include systemic treatments (chemo-embolisation will not be deemed to be a previous treatment line) whereas treatment lines during the study will be deemed to be as such whether they are systemic or locoregional treatments (chemo-embolisation will be deemed to be a treatment line in this case).

Treatment with Lutathera will be considered to be metabolic radiotherapy.

If the combination involves a somatostatin analog (as the main treatment), then the combination becomes the main treatment unless surgery is involved. The start date of the main treatment is the date of the visit recording the combination (and this same date will be considered as the discontinuation date of the previous line). The discontinuation of the main treatment also corresponds to the date when the treatment was discontinued before starting a new line.

Moreover, if Pazopanib is recorded as the previous "other" treatment it should then be reclassified as targeted therapy and presented as the 3rd targeted therapy line (in addition to Everolimus and Sunitinib).

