5.4.3. Representativeness of Samples of Doctors and Patients

Comparisons will be made between active doctors who took part in the study (who included at least one patient) and inactive doctors who did not include any patients, by calculating standardised differences.

These standardised differences will be calculated as follows:

Type of variable	Equation			
Qualitative	$d = \frac{P_1 - P_2}{\sqrt{\frac{P_1(1 - P_1) + P_2(1 - P_2)}{2}}}$			
	P ₁ : proportion of individuals with the feature in group 1			
	P ₂ : proportion of individuals with the feature in group 2			
Quantitative	$d = \frac{\text{moy}_1 - \text{moy}_2}{\sqrt{\frac{\text{var}_1 + \text{var}_2}{2}}}$			
	mean ₁ : mean in group 1			
	mean ₂ : mean in group 2			
	var ₁ : variance in group 1			
	var ₂ : variance in group 2			

Similarly, comparisons will be made between included and non-included patients based on information collected in the non-inclusion register (age, sex), The reasons for non-inclusion will be presented. The "others" reasons for non-inclusion will be listed.

In addition, patients who are lost to follow-up and/or dropped out of the study (for a reason other than death) will be compared to patients with complete follow-up (follow-up until progression, death, end of main treatment ongoing at the time of inclusion or 2-year cutoff date) in the reference set.

We will deem the observed difference to be small if the standardised difference is between [0.2 and 0.3], average if between [0.3-0.8] and large if it is over 0.8. A value of 0.2 or less will be considered to represent no difference.

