8. KEY E-CRF DATA

The table below shows the data required in the eCRF to conduct the main study analysis. As stated in the part describing this analysis (See Section 5.5), particular attention will be paid to recording data on disease progression in the study patients in order to reduce bias.

Parameter	Data	eCRF Variables
Group (documented treatment in	Main treatment	ITTTRTC
the study)	Precision	EVESUNC
Start date (of line ongoing at the	Treatment start date	TSUINDT
time the patient was included) of		TINITDT
treatment with targeted therapy or other treatments		TCHINDT
Disease outcome	Response to treatment, date	Tumour assessment visits:
		Radiological response:
		EXTRESP
		EXTP1DT
		Clinical response:
		EXTCRYN
		EXTCRSP
		EXTP2DT
		Dropped out of study:
		STTRESP
		STTREDT
	Death, date	Dropped out of study:
		STTSTAT
		STTDTDT
Patient status at the end of the	Patient status	Dropped out of study:
study	2-year follow-up completed	STTSTAT
		Complete follow-up:
		VISLVYN
Total duration of exposure to	Treatment start date	TSUINDT
treatment		TINITDT
		TCHINDT
	Treatment end date	FTTEND
	(permanent discontinuation)	
Temporary discontinuations	Discontinuation	TSUTSYN, TEVTSYN, TIXTSYN, TCHTSYN,
		TASTSYN, PTST2YN
	Date discontinuation started	TSTOPDT
	Reason for discontinuation	TSTOPRS
	Duration of discontinuation	TSTOPDU
Permanent discontinuations	Date of permanent discontinuation	FTTEND

Parameter	Data	eCRF Variables
	Reason for permanent discontinuation	FTTENRS
Adverse events	Description	AEVTERM
	Seriousness	AEVSERC
	Relationship with treatment	AEVRELC
	Death	AEVAES1
	Action on treatment	AEVACTC
	Grade	AEVGRAD

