	[Q1; Q3]	[XX.X; XX.X]	[XX.X; XX.X]	[XX.X; XX.X]
Number of patients per centre (N(%))	N	XX	XX	XX
	1	XX (XX.X%)	XX (XX.X%)	XX (XX.X%)
	2	XX (XX.X%)	XX (XX.X%)	XX (XX.X%)
		XX (XX.X%)	XX (XX.X%)	XX (XX.X%)

Table 14.1.3.4: Reasons for Dropping Out of the Study – Safety Analysis Set

		Targeted therapies (N=XX)	Other treatments (N=XX)	Treatment not stated (N=XX)	Total (N=XX)
Study drop-out	N Missing data Yes	XX XX XX (XX.X%)	XX XX XX (XX.X%)	XX XX XX (XX.X%)	XX XX XX (XX.X%)
	No	XX (XX.X%)	XX (XX.X%)	XX (XX.X%)	XX (XX.X%)
Reason for dropping out of the study (1)	N Missing data	XX XX	XX XX	XX XX	XX XX
	Alive >>>	XX (XX.X%) XX (XX.X%) XX (XX.X%)			
	Lost to follow-up Death >> Progression of the disease >> Adverse event	XX (XX.X%) XX (XX.X%) XX (XX.X%) XX (XX.X%)			

⁽¹⁾ Percentages calculated as a proportion of patients who dropped out of the study.

Table 14.1.3.5: Reasons for Dropping Out of the Study - Reference Set

		Targeted therapies (N=XX)	Other treatments (N=XX)	Treatment not stated (N=XX)	Total (N=XX)
Study drop-out	N Missing data Yes No	XX XX XX (XX.X%) XX (XX.X%)	XX XX XX (XX.X%) XX (XX.X%)	XX XX XX (XX.X%) XX (XX.X%)	XX XX XX (XX.X%) XX (XX.X%)
Reason for dropping out of study (1)	N Missing data Alive >> >> Lost to follow-up >> Progression of the disease >> Adverse event >> Missing data >> Alive Failure to meet the inclusion- non-inclusion criteria at inclusion into the study Patient decision	XX XX XX (XX.X%) XX (XX.X%) XX (XX.X%) XX (XX.X%) XX (XX.X%) XX (XX.X%) XX (XX.X%) XX (XX.X%) XX (XX.X%)	XX XX XX (XX.X%) XX (XX.X%) XX (XX.X%) XX (XX.X%) XX (XX.X%) XX (XX.X%) XX (XX.X%) XX (XX.X%) XX (XX.X%)	XX XX XX (XX X%) XX (XX X%)	XX XX XX (XX.X%) XX (XX.X%) XX (XX.X%) XX (XX.X%) XX (XX.X%) XX (XX.X%) XX (XX.X%) XX (XX.X%) XX (XX.X%)

⁽¹⁾ Percentages calculated as a proportion of patients who dropped out of the study.

TABLE 14.1.3.6: PATIENT STATUS AT THE END OF THE STUDY – SAFETY ANALYSIS SET

		Targeted therapies (N=XX)	Other treatments (N=XX)	Treatment not stated (N=XX)	Total (N=XX)
Status	N	XX	XX	XX	XX
Status	Missing data	XX	XX	XX	XX
	Alive	XX (XX.X%)	XX (XX.X%)	XX (XX.X%)	XX (XX.X%)
	>> 2-year follow-up completed (1)	XX (XX.X%)	XX (XX.X%)	XX (XX.X%)	XX (XX.X%)
	>> Failure to meet the inclusion-non-				
	inclusion criteria at inclusion into the	XX (XX.X%)	XX (XX.X%)	XX (XX.X%)	XX (XX.X%)
	study				
	>> Patient decision	XX (XX.X%)	XX (XX.X%)	XX (XX.X%)	XX (XX.X%)

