9.4. Safety Data

9.4.1. Treatment Drop-outs and Reasons for Dropping Out Documented for the Study

Table 14.3.1.1: Total Duration of Exposure to the Main Treatment Received at the Inclusion Since Starting the Documented Treatment in the Study – Safety Analysis Set

		Targeted therapies (N=XX)	Other treatments (N=XX)	Total (N=XX)
Total duration of treatment exposure (months)	N	XX	XX	XX
	Missing data	XX	XX	XX
	Mean (SD)	XX.XX (X.XX)	XX.XX (X.XX)	XX.XX (X.XX)
	Median	XX.X	XX.X	XX.X
	[Min; Max]	[XX.X; XX.X]	[XX.X; XX.X]	[XX.X; XX.X]
	[Q1; Q3]	[XX.X; XX.X]	[XX.X; XX.X]	[XX.X; XX.X]
Total duration of treatment exposure (N(%))	N	XX	XX	XX
	Missing data	XX	XX	XX
	[0-3] months	XX (XX.X%)	XX (XX.X%)	XX (XX.X%)
	[3-6] months	XX (XX.X%)	XX (XX.X%)	XX (XX.X%)
	[6-12] months	XX (XX.X%)	XX (XX.X%)	XX (XX.X%)
	[12-24] months	XX (XX.X%)	XX (XX.X%)	XX (XX.X%)
	> 24 months	XX (XX.X%)	XX (XX.X%)	XX (XX.X%)

Total duration of exposure = (Date of last dose of treatment – Date of first dose of treatment +1)/30.4375.

For patients still on treatment at 2 years, the date of the last treatment dose used is the date of the last visit.

For patients who dropped out of the study, the date of the last treatment dose used is the date of the last visit.

Using the same template:

Table 14.3.1.2: Total Duration of Exposure to the Main Treatment Received at the Inclusion Since Starting the Documented Treatment in the Study – Reference Set

Table 14.3.1.3: Total Duration of Exposure to the Treatment Received at Least Once During the Study – Safety Analysis Set

Add the footnote: As the start/end dates of combinations reported during a treatment line are not available, the visit dates were used to calculate the duration of the combination treatments. Exposure to combinations is overestimated.

Table 14.3.1.4: Total Duration of Exposure to the Treatment Received at Least Once During the Study – Reference Set

Table 14.3.1.5: Temporary Discontinuations of the Main Treatment at Inclusion Documented in the Study – Safety Analysis Set

		Targeted therapies (N=XX)	Other treatments (N=XX)	Total (N=XX)
At least one temporary discontinuation	N	XX	XX	XX
	Missing data	XX	XX	XX
	Yes No	XX (XX.X%) XX (XX.X%)	XX (XX.X%) XX (XX.X%)	XX (XX.X%) XX (XX.X%)
Number of temporary discontinuations per patient	N	XX	XX	XX
	Missing data	XX	XX	XX
	Mean (SD)	XX.XX (X.XX)	XX.XX (X.XX)	XX.XX (X.XX)
	Median	XX.X	XX.X	XX.X
	[Min; Max]	[XX.X; XX.X]	[XX.X; XX.X]	[XX.X; XX.X]
	[Q1; Q3]	[XX.X; XX.X]	[XX.X; XX.X]	[XX.X; XX.X]

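### The exposure rule for early drop-outs overrides a recorded treatment stop date and conflicts with the end date the SAP lists for exposure

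*SAP*

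**What the plan says.** SAP 4.7 computes total exposure in months as (date of last receipt − date of first receipt + 1)/30.4375. For early study drop-outs it sets the end date: "the date of last receipt of the treatment considered will be the date of the last visit". The footnote to Table 14.3.1.1 (SAP 9.4.1) says the same: "For patients who dropped out of the study, the date of the last treatment dose used is the date of the last visit". Neither statement carries a condition.

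The footnote sentence just before it does carry one: "For patients still on treatment at 2 years, the date of the last treatment dose used is the date of the last visit".

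Death is a reason for dropping out. Table 14.1.3.4 (SAP 9.1.3) lists, under reasons for leaving the study, "Lost to follow-up Death >> Progression of the disease >> Adverse event". Where the SAP wants deaths left out of the drop-outs it says so, as in section 5.4.3: "dropped out of the study (for a reason other than death". Section 4.7 makes no such exclusion.

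SAP section 8 points to a different end date. Its row for total duration of exposure lists the start date and a treatment end date, glossed as permanent discontinuation, under the variable FTTEND. The row for permanent discontinuations uses the same variable for the "Date of permanent discontinuation".

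**The concern.** Patients remain in the study after stopping the inclusion treatment. The case report form (Protocol appendix, CRF section 3.3) keeps a patient with no current treatment under observation up to two years unless the patient dies or is lost. The last visit can therefore fall many months after the last dose. For such a patient the rule in 4.7 counts untreated follow-up as exposure, although the CRF asks for the date of definitive stop (CRF Table 5).

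The SAP describes itself as the reference document for all analyses, so a programmer who follows 4.7 and the footnote would overwrite a recorded date. Total exposure is the first item in SAP 5.7.1, within the safety part of the primary objective. It is tabulated by treatment group, by treatment received and by ECOG.

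**Working it through.** The documents state no exposure figure, so there is none to reproduce. The check applies the SAP formula to single cases and then asks how large the net error could be.

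**Single cases** (1 month = 30.4375 days, start at day 0):

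- Stop at month 3, last visit at month 18, then drop-out. Under the rule: (18 × 30.4375 + 1)/30.4375 = 18.03 months. With the recorded stop: (3 × 30.4375 + 1)/30.4375 = 3.03 months. Excess 15.0 months.
- Stop at month 12, last visit at month 18: 18.03 against 12.03. Excess 6.0 months.
- Last visit at month 10, death on treatment at month 12: 10.03 against 12.03. Here the rule understates by 2.0 months.

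The error therefore runs in both directions. It is an overstatement if treatment stopped before the last visit, and a small understatement if treatment continued beyond it.

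**Agreement between tables.** Table 14.3.1.7 reports time from initiation to permanent discontinuation. The first patient above would contribute about 3 months there and 18 months in Table 14.3.1.1.

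**Net size.** The documents give neither the time to stopping nor the drop-out rate in this cohort, so both are assumed and varied:

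- Median time to stop: 6, 11 or 18 months.
- Median time to drop-out or death: 24, 38 or 60 months. The middle value is the overall pNET survival median cited in the protocol's introduction.
- Visits every 2 or 3 months (SAP 3.3), with 24 months of follow-up.
- Both times exponential and independent, counted from treatment start, with 400,000 simulated patients per scenario.

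True end of treatment is the earlier of stop and drop-out; the rule's end is the last visit before drop-out. Errors are in months. Paired figures are for visits every 2 / 3 months.

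| Median to stop | Median to drop-out | Drop-outs | Of these, stopped before last visit | Net error per drop-out | Net error over all patients |
|---|---|---|---|---|---|
| 6 | 24 | 50% | 57% / 54% | +4.34 / +3.84 | +2.17 / +1.92 |
| 6 | 38 | 36% / 35% | 59% / 56% | +4.68 / +4.16 | +1.66 / +1.47 |
| 6 | 60 | 24% | 60% / 58% | +4.87 / +4.43 | +1.18 / +1.07 |
| 11 | 24 | 50% | 41% / 39% | +2.66 / +2.15 | +1.33 / +1.07 |
| 11 | 38 | 35% | 42% / 41% | +2.88 / +2.39 | +1.02 / +0.85 |
| 11 | 60 | 24% | 43% / 42% | +3.02 / +2.53 | +0.73 / +0.61 |
| 18 | 24 | 50% | 29% / 27% | +1.50 / +1.01 | +0.75 / +0.51 |
| 18 | 38 | 35% | 30% / 29% | +1.69 / +1.20 | +0.60 / +0.42 |
| 18 | 60 | 24% | 31% / 30% | +1.78 / +1.30 | +0.43 / +0.31 |

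The last column is the net error per drop-out times the drop-out proportion, for example 4.34 × 0.50 = 2.17. Across scenarios, drop-outs who had stopped before their last visit were overstated by 7.5 to 8.75 months on average. The other drop-outs were understated by 0.92 to 1.44 months.

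**The case against.** The best defence is that the last-visit rule was meant as a fallback. Section 8 already names FTTEND as the end of exposure. In the footnote the drop-out sentence follows one about patients still on treatment, so the pair may be intended for patients with no end date. SAP 5.7.1 also sums exposure over separate periods of the same treatment, which makes little sense if each line of a drop-out ran to the last visit. This is probably what the authors intended. But no passage gives FTTEND precedence, and the condition written for two-year completers is missing for drop-outs. The defence explains the conflict without removing it.

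It is also fair to say that the consequences are contained. Adverse event percentages use patient counts as denominators and have their own on-treatment window (SAP 5.7.2). PFS and OS have their own event and censoring dates (SAP 5.5.1). Table 14.3.1.7 still reports time to permanent discontinuation for those who stopped.

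A reader might infer three stronger things that the documents do not support:

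- That every early drop-out is overstated. Those still on treatment at their last visit are not.
- That the sickest patients will look longest treated. A drop-out's exposure is capped at an early last visit. In one assumed scenario (line median 11 months, post-line survival median 18 months, about 15% withdrawn or lost by 24 months) the literal rule gave mean exposure of about 11.8 months in drop-outs and 15.1 in completers. The order reversed only with a line median of 6 months. Nothing was worked out by ECOG.
- That the drop-out sentence stands under every exposure table. It is printed only under Table 14.3.1.1. The notes to ECOG Tables 14.3.1.9 and 14.3.1.10 carry only the two-year sentence, although the general rule in 4.7 would still apply to them.

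**Conclusion.** The point holds: the rule is wrong as written and conflicts with SAP section 8. The individual error can be large. The net error was an overstatement in every scenario tried, about +1.0 to +4.9 months per drop-out and +0.3 to +2.2 months averaged over all patients. Those sizes rest on assumed stopping and drop-out rates, on independent exponential times, and on counting every patient from treatment start as if incident. They show the plausible scale and are not a forecast for this cohort. The SAP's existing note that exposure is overestimated concerns combination treatments only, so it does not disclose this error.

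**What to change.** In SAP 4.7, and in the footnotes to the exposure tables (14.3.1.1 to 14.3.1.4 and 14.3.1.9 to 14.3.1.11), state that exposure to each treatment ends at its recorded permanent discontinuation date (FTTEND) whenever there is one. The last visit date is used only if the treatment was still ongoing, with no recorded stop date, when the patient left the study. Tables 14.3.1.5 to 14.3.1.8 report discontinuations and need no change.

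The cost is one sentence, aligned footnotes and a small change in the derivation; no new data are needed. Patients who leave on treatment with no recorded stop will still be understated by the gap since their last visit, which a footnote can say.
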